- 1. **Self-reported individual symptoms at day 5 on the SSPedi instrument**: For each of the 15 ordinal outcomes representing symptoms (scored 0-4), a proportional odds model will be fitted using the corresponding baseline symptom score, participant age and treatment as covariates. As some individual symptoms may be uncommon, to avoid specifying models that may be overfitted for those symptoms, these models will use only this minimal set of three covariates. The estimated odds ratio for the intervention (representing the odds of having a higher versus lower score in the intervention group) will be estimated and presented along with a 95% CI.
- 2. **Faces Pain Scale-Revised**: In keeping with common practice, this 6-point scale (scores of 0, 2, 4, 6, 8,10) will be treated as a continuous variable and analyzed using ANCOVA in the same way as the primary SSPedi outcome. To check the sensitivity of the substantive finding (i.e., whether the conclusion about efficacy is the same) to the analytic method, the analysis will be repeated using the same ordinal model used for the individual SSPedi components.
- 3. **PedsQL 3.0 Acute Cancer Module domain scores**: Each of these 8 scores will be treated as continuous variables and analyzed using ANCOVA in the same way as the primary SSPedi outcome.
- 4. **Documentation of symptoms on day 5 (±1 day):** Analyses will involve three analyses for each symptom class. Each analysis will fit a logistic regression model to estimate the odds ratio for documentation (on day 5 ±1 days) comparing intervention groups, adjusting for age and treatment. It is possible that there will be too few documentation events to reliably fit this three-parameter model to a sufficient number of the 15 symptoms. To be consistent across analyses of symptoms, if more than 5 of the 15 symptoms have fewer than 30 documentation events for any of analyses a, b, or c below, all treatment effects here will be estimated by a simple difference in the proportions with documentation, p-values will be computed from the Fisher exact test, and 95% confidence intervals will use the Newcombe method.
 - a. Each participant will be classed as having the symptom documented or not. All participants are included in the analytic sample for each symptom.
 - b. The analytic sample will be limited to those participants who self-report the symptom on the day 5 SSPedi (symptom score > 0).
 - c. The analytic sample will be limited to those participants who have the most bothersome self-report of the symptom on the day 5 SSPedi (symptom score ≥ 3).
- 5. Interventions for symptoms: Analyses will follow a similar flow to the analyses of documentation of symptoms. For each of the 15 symptoms, each participant will be classified as having an intervention at day 5 (±1 days). Also collected is whether interventions were administered specifically for the specific symptoms. For example, acetaminophen may be administered for fever or pain. As interventions are expected to be more uncommon than symptoms, all treatment effects will be estimated by simple differences in the proportions with interventions, p-values will be computed from the Fisher exact test, and 95% confidence

intervals for differences in proportions will use the Newcombe method.

- a. Each participant will be classed as having an intervention for the symptom or not. All participants are included in the analytic sample for each intervention-symptom pair.
- b. The analytic sample will be limited to those participants who self-report the symptom on the day 5 SSPedi (symptom score > 0).
- c. The analytic sample will be limited to those participants who have the most bothersome self-report of the symptom on the day 5 SSPedi (symptom score ≥ 3).

Missing Data: The PedsQL will be scored according to its scoring guide, which includes rules for scoring in the presence of missing elements on each domain modules. No other deterministic rule-based method will be used to deal with missing data.

If more than 5% are missing data on data needed to fit any of the analytic models (for the primary outcome, individual symptom scores, Faces Pain Scale-Revised, and PedsQL 3.0 Acute Cancer Module domain scores) the results for that model will use multiple imputation. A set of 20 complete datasets will be generated using separate within-treatment-group imputation models. These models will include all the study outcomes listed just above, and the key covariates that appear in our adjustment models (age, treatment, diagnosis group and relapse status). The models will be fitted in each imputed dataset and the pooled estimate of the treatment effect and its standard error will be computed using Rubin's rules.

Analyses of documentation and interventions will not use any imputation. There can be no missing data for these outcomes: if a symptom is not documented in the health record and there is no record of an intervention being used, then this constitutes a 'no' for the outcome. While it is possible that the SSPedi symptom score needed for the identification of the analytic datasets in analyses (4b, 4c, 5b, and 5c) is missing for some participants, the more exploratory nature of these analyses led us to the decision to use only observed data for these outcomes.

We will conduct one end-of-study analysis. There are no planned subgroup analyses.

Justification for Methodological Choices

A lower age limit of 8 years was chosen as this is the youngest age for which SSPedi has been validated. However, in parallel work, we have developed a proxy (2-7 years) and self-report (4-7 years) version of SSPedi for younger children and we are currently evaluating the reliability and validity of these instruments. Future work will expand SPARK using these tools in development.

We plan to conduct this study among English-speaking children because SSPedi is currently only available in English. Translation to other languages is in progress and future work will expand SPARK to include other languages.

INNOVATION, KNOWLEDGE TRANSLATION AND FUTURE PLANS

Innovation and Knowledge Translation and Exchange (KTE)

An innovative approach throughout our research program is the engagement with choice architecture experts to enhance the design of SPARK. Choice architecture is important as context can be created to nudge people into actions.^{29,39} For instance, the layouts, message framing, visual elements and other contextual cues in the SPARK platform have been optimized to maximize the likelihood that the platform is used and the material is understood. We will continue to incorporate choice architecture input as we execute the trial.

The targets of our KTE efforts are patients, families, healthcare providers and decision makers including hospital and governmental administrators.

Integrated KTE: To increase awareness and to engage with a variety of stakeholders, we will create an Advisory Panel. The Panel will include two childhood cancer survivors, one parent of a child with

Page 9 of 13

SPARK RCT Protocol

cancer, healthcare providers and hospital administrators. We will meet face-to-face or by teleconference at least annually to discuss progress and identify opportunities for KTE.

End of Grant KTE: We will publish the results of this study in peer-reviewed journals (minimum of 3 mid to high impact journals) and support attendance at national and international conferences. We plan to distribute plain language summaries throughout the Children's Oncology Group (COG), the C17 Research Network (represents the 17 centers in Canada) and the Pediatric Oncology Group of Ontario (represents the 5 centers in Ontario). We also plan to hold regular webinars and podcasts. The SickKids Industry, Partnerships and Commercialization office will help promote SPARK as a no cost web-portal for hospital use within Canada, offering the license to purchase to use the platform, technical support and data management outside of Canada. In order to further enhance KTE, we will create an end-of-grant report which summarizes the processes refined to achieve symptom screening and symptom feedback to providers. This report will include the steps taken, challenges encountered and solutions to those challenges. This report will help other institutions to implement the approach expeditiously.

Future Plans

Upon completion of this trial, we will use the information garnered to propose an incrementally more complex RCT in which we will achieve electronic health records integration of symptom data and create actions in the health records based upon high symptom scores. It is premature to undertake this trial in pediatric oncology at present as 3 of our 8 sites do not yet have computerized physician order entry. Further, achieving electronic health records integration will require years of preparatory work; we plan to conduct this work alongside this trial such that the next RCT will include electronic health record integration. This next trial will also include ambulatory patients with remote symptom screening from home.

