The primary and secondary PROs will be measured by patient self-report while documentation of symptoms and intervention provision will be abstracted from the health record. Self-reported PROs and QoL measures are essential in this study as the intervention is focused on reducing symptom burden.

Sample Size Justification

We used data from our SSPedi validation study for power calculations.⁴ We recruited 302 children who were hospitalized and expected to be in hospital or in clinic 3 days later. Children completed SSPedi on days 1 and 4 and a 5-point global symptom change scale on day 4. The average absolute change in total SSPedi scores for those who rated they were a little worse or a little better (1-point change) was 2.7 which is the minimally clinically important difference. The average standard deviation of the two total SSPedi scores (on days 1 and 4) was 8.5. Thus, with 80% power and alpha of 0.05, we will require 157 patients per group or 314 patients total. Assuming 10% will be non-evaluable, we will recruit 345 total.

Recruitment

All 8 participating institutions enrolled patients in our previous SSPedi validation study; all have experience with SSPedi, recruited patients in a timely fashion and submitted high quality data. Investigator calls twice a month will focus on recruitment status and enrollment issues. Specific outreach to each institutional principle investigator and clinical research associate will be made in the event of lagging accrual and a specific plan to rectify accrual will be made. If accrual continues to lag, the institution may be replaced.

Table 1 shows the number of expected eligible participants at the 8 sites; estimates were based on our pilot study. We anticipate 160 eligible patients per year. Thus, assuming that at least 60% of patients are identified and consent, we will complete enrollment within 4 years although accrual may take longer given the COVID-19 pandemic. Data analysis and knowledge dissemination will occur in year 5.

Table 1: Site (PI): Number new cancer	Year 1	Year 2	Year 3	Year 4	Year 5
patients annually (all ages)	Enroll	Enroll	Enroll	Enroll	
Toronto ([name]): 300-350	80	80	80	80	Analyze
Vancouver ([name]): 120-160	30	30	30	30	
Winnipeg ([name]): 40-60	10	10	10	10	Publish
London ([name]): 55-70	10	10	10	10	
Hamilton ([name]): 65-80	10	10	10	10	KTE
Ottawa ([name]): 55-70	10	10	10	10	
Halifax ([name]): 55-70	10	10	10	10	
Edmonton ([name]) 40-70	10	10	10	10	
TOTAL	170	170	170	170	

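### Fisher exact p-values beside Newcombe intervals in outcomes 4 and 5 give up some power and can disagree, with no rule for which leads

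*Combined protocol and SAP*

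**What the plan says.** Under ANALYTIC PLAN, secondary outcome 5 (interventions for symptoms) sets one method for every comparison: "all treatment effects will be estimated by simple differences in the proportions with interventions, p-values will be computed from the Fisher exact test", and "intervals for differences in proportions will use the Newcombe method". No condition is attached.

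Secondary outcome 4 (documentation of symptoms) starts from logistic regression adjusted for age and treatment. It switches all its comparisons to the unadjusted difference "if more than 5 of the 15 symptoms have fewer than 30 documentation events for any of analyses a, b, or c below". In that case "p-values will be computed from the Fisher exact test, and 95% confidence intervals will use the Newcombe method", the same pair as in outcome 5.

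Each outcome is analysed in three samples ("Analyses will involve three analyses for each symptom class"): all participants, those reporting the symptom on day 5, and those scoring 3 or more. That makes 15 symptoms × 3 samples × 2 outcomes = 90 comparisons.

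The plan does not say whether the Newcombe interval carries a continuity correction. It does not say whether the p-value or the interval leads if they disagree. The Missing Data paragraphs call analyses 4b, 4c, 5b and 5c more exploratory (4 × 15 = 60 comparisons); 4a and 5a are not so labelled.

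**The concern.** The test and the interval come from different constructions. Fisher's test conditions on both margins and guarantees its level by being conservative, most of all when events are few. The Newcombe interval is built from two Wilson score intervals, carries no such guarantee, and is usually less conservative.

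Two things are at stake. First, Aim 3 has most room for improvement where documentation and intervention are now rare, and there Fisher gives up the most power. Second, a row can show p>0.05 next to an interval that excludes no difference. With no rule on which leads, that choice would be made after the data are seen.

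**Working it through.** **1. The plan's own figure.** No size, power or event count is given for Aim 3. The only design figure is for the primary outcome: "Thus, with 80% power and alpha of 0.05, we will require 157 patients per group or 314 patients total". With a difference of 2.7 and SD 8.5, n = 2 × [8.5 × (1.960 + 0.842) / 2.7]² = 155.6, so 156 per arm against the stated 157, which is close enough. 314 × 1.10 = 345.4, against 345 recruited. I use 157 per arm for the full sample, and assume a two-sided nominal 5% because none is stated for Aim 3.

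**2. Will the outcome 4 fallback apply?** The Preliminary Data give documentation of 0%, 3%, 4%, 7%, 10% and 10% for six symptoms among children with at least medium bother. The Background gives severe fatigue in 33%. If a symptom is severe in 33% of 314 children, sample c holds 103.6 of them. At 10% documented that is 10.4 events. At 10% in one arm and 30% in the other it is 51.8 × 0.10 + 51.8 × 0.30 = 20.7. Six symptoms below 30 events are enough, so the fallback is very likely.

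**3. Two rows by hand.** The Newcombe limits are d − √[(p₁−l₁)² + (u₂−p₂)²] and d + √[(u₁−p₁)² + (p₂−l₂)²], where l and u are Wilson limits.

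- 5/157 against 0/157. Fisher p = 2 × (157·156·155·154·153)/(314·313·312·311·310) = 0.061. The Wilson limits are 0.0137 to 0.0724 and 0 to 0.0239. The lower limit is 0.0318 − √(0.0182² + 0.0239²) = 0.002 and the upper is 0.072. So p>0.05 stands beside an interval of 0.2% to 7.2%.
- 4/57 against 0/63. Fisher p = (57·56·55·54)/(120·119·118·117) = 0.048. The opposite extreme table is more probable, so it is not added. The Newcombe interval is −0.1% to 16.7%. Here the disagreement runs the other way.

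**4. Exact size.** For each pair of arm sizes I enumerated every 2×2 table and summed binomial probabilities over those with Fisher p≤0.05.

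| Arms | rate 3% | 10% | 18% | 62% | maximum |
|---|---|---|---|---|---|
| 157/157 | 1.9% | 3.3% | 3.5% | 3.9% | 3.9% |
| 155/159 | 3.0% | 3.9% | 4.3% | 4.5% | 4.5% |
| 35/35 | 0.04% | 1.3% | 2.4% | 2.9% | 2.9% |
| 33/37 | 0.6% | 3.0% | 3.5% | 3.8% | 3.9% |

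**5. Power.** Same enumeration under unequal rates. Boschloo's test uses the two-sided Fisher p-value as its statistic and rejects when that value is ≤c. Here c is the largest cut-off for which the rejection probability, maximised over a common rate, is ≤5% (c = 0.0626 at 157/157, maximum size 4.96%). Since c is at least 0.05, it rejects whenever Fisher does.

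| Arms | true rates | Fisher | Boschloo | Newcombe excludes 0 |
|---|---|---|---|---|
| 157/157 | 3% v 10% | 65% | 69% | 72% |
| 157/157 | 10% v 20% | 65% | 69% | 70% |
| 157/157 | 18% v 30% | 66% | 70% | 71% |
| 157/157 | 0% v 5% | 80% | 90% | 90% |
| 155/159 | 3% v 10% | 67% | 68% | 71% |
| 155/159 | 10% v 3% | 71% | 74% | 72% |
| 60/60 | 0% v 10% | 56% | 73% | 73% |
| 50/50 | 0% v 10% | 38% | 57% | 57% |

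**6. Expected disagreements among 90 rows** (uncorrected interval; unstated symptom rates assumed between 10% and 94%; rises of 5 to 20 points in the intervention arm).

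| Arms in samples a, b, c | no effect | with effects |
|---|---|---|
| 172, 80, 33 each (equal) | 1.5 | 3.9 to 5.6 |
| 171/174, 83/77, 30/36 | 0.7 | 1.8 to 2.3 |

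Under no effect the chance of three or more such rows is 18% and 4% respectively, treating rows as independent although the samples are nested. A continuity-corrected interval gives 0.2 to 0.7 rows with equal arms, but 0.6 to 2.7 with the unequal arms, so it is no sure cure.

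**The case against.** The strongest reply is that Fisher does what it promises: type I error stays at or below nominal. With up to 90 comparisons and no multiplicity adjustment described, some conservatism is welcome. Items 4 and 5 set no significance threshold, so no declared conclusion turns on p=0.052. For outcome 4 the pair is only a fallback. Much of the shortfall is discreteness rather than the choice of test: at a 3% rate the Newcombe interval's own non-coverage is 3.75% at 157 per arm, 1.2% at 60 and 0.26% at 35.

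Most of this stands, and it keeps the point minor. It does not defend the pairing. Boschloo's test gives the same guarantee without losing power to Fisher, and conservatism that varies with event rate and arm balance is not a multiplicity plan.

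A reader might infer three stronger things that the documents do not support:

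- That the tables will contradict themselves in several rows. The expected count is near 1 with no effect. It reaches several only with real effects in most rows, near-equal arms and the uncorrected interval.
- That the disagreement always has the interval excluding zero. The 4/57 against 0/63 row shows otherwise, and samples b and c are defined by day 5 scores, so equal arms there would be chance.
- That the error rate or the main result is compromised. Neither is.

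**Conclusion.** The point holds as a minor matter of efficiency and coherence. The Fisher and Newcombe pair is fixed for 45 comparisons and very likely for 45 more. Fisher runs below its nominal level, clearly so at low rates and in small subsets, and less so with common symptoms or slightly unequal arms. Against the Newcombe decision the power cost is about 4-7 points for most low-rate comparisons with equal arms of 157 (10 points for 0% v 5%). It is often smaller with slightly unequal arms, and about 17-18 points in the sparsest subsets tried. Disagreeing rows number about 1-2 of 90 with no effect and about 2-5 with effects, usually but not always with the interval excluding zero.

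This rests on a two-sided 5% level, subset sizes of about 80 (sample b) and 33 to 60 (sample c) per arm, and assumed rates for the symptoms whose rates are not given. The primary analysis is unaffected.

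**What to change.** In items 4 and 5, replace Fisher's exact test with Boschloo's exact unconditional test, ordering tables by the two-sided Fisher p-value; the guarantee of never losing power to Fisher belongs to that version. Name the interval as the Newcombe hybrid-score interval without continuity correction. Add that the estimate with its interval leads if the two disagree.

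The cost is a few words in the SAP and slightly more computation; no new data are needed. Boschloo's test is less familiar to readers. It reduces disagreements without removing them: both rows with Fisher p just above 0.05 at 157 per arm (5 v 0 and 11 v 3) become significant, but it still differs from Newcombe in 0-4% of samples in the equal-arm cases tried. With unequal arms the benefit varies. At 155/159 with 0% v 5% it gained nothing in either allocation, and with the 5% rate in the larger arm it still differed from Newcombe in about 9% of samples. That is why the rule on which result leads is needed as well.

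Fisher's mid-p value is the alternative. It usually recovers slightly more power, but its size can reach about 5.5% and it does not guarantee agreement with Newcombe when arms are unequal, so it is a trade-off rather than a plain improvement.

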Control Arm: Participants randomized to the control arm will not complete daily symptom screening. They will complete SSPedi on days 1 and 5 to obtain the primary outcome. Health care providers will not be notified of their SSPedi scores and no symptom reports or symptom alerts will be generated.

For both study groups participant's guardian will be asked to fill out a household demographic form.

Allocating Participants

The allocation sequence will be computer generated and will be concealed from all participants, healthcare providers and research team members. Consenting participants will be randomized 1:1 to intervention vs. control groups using permuted block sizes and stratified by treatment (stem cell transplant yes vs. no) and age (8-10, 11-14 and 15-18 years) as our previous data suggested that these factors were the most strongly associated with higher total SSPedi scores. Assignment of enrolled participants will be communicated by email to the institutional principal investigator and clinical research associate following randomization.

Protecting against Bias

We hypothesize that the key elements to improving symptom control will be: (1) the systematic measurement of bothersome symptoms; (2) providing this information to healthcare providers; and (3) improving access to supportive care CPGs for providers. Given that this trial is randomized at the individual level and not at the cluster level, clinicians caring for patients in the control group may be more aware of supportive care CPGs. Although this information does represent contamination, we hypothesize that without a mechanism for children and adolescents to report symptoms, this level of contamination will not substantially influence the effectiveness of the intervention. However, we will measure documentation of symptoms and provision of interventions to facilitate interpretation of trial

results. We are not conducting a cluster randomized trial because there are only 17 centers in Canada that treat children with cancer, and site numbers and logistical challenges preclude this study design.

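### Analyses 4b, 4c, 5b and 5c compare the arms within children selected by their day-5 symptom score, an outcome the intervention is meant to change

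*Combined protocol and SAP*

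**What the plan says.** Under Analytic Plan, secondary outcomes 4 and 5 each have three analysis sets for each of the 15 symptoms. Sets 4a and 5a include every participant. Of 4b the plan says "The analytic sample will be limited to those participants who self-report the symptom on the day 5 SSPedi" (score above 0), and 5b is worded the same way. Sets 4c and 5c are "limited to those participants who have the most bothersome self-report of the symptom on the day 5 SSPedi" (score of 3 or more).

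Between-arm inference is planned in all of them:

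- Outcome 4, default: "Each analysis will fit a logistic regression model to estimate the odds ratio for documentation", adjusted for age and treatment.
- Outcome 4, sparse-event fallback: "all treatment effects here will be estimated by a simple difference in the proportions with documentation", with Fisher p-values and Newcombe 95% intervals.
- Outcome 5: "all treatment effects will be estimated by simple differences in the proportions with interventions", with the same test and interval and no adjustment.

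Under Missing Data, the plan says of 4b, 4c, 5b and 5c that "the more exploratory nature of these analyses led us to the decision to use only observed data for these outcomes". The section closes with "There are no planned subgroup analyses". Under Protecting against Bias, the protocol says "we will measure documentation of symptoms and provision of interventions to facilitate interpretation of trial" results. No passage notes that membership of these subsets is determined after randomization.

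**The concern.** The selecting variable is a trial outcome. Individual day-5 symptom scores are secondary outcome 1, and the hypothesis under Objectives is that the intervention improves specific symptoms. If it does, the children scoring above 0, or 3 or more, on day 5 are a different kind of child in each arm, and randomization no longer protects the comparison.

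The design supplies a concrete route. In the intervention arm only, reports go to the team daily, and on days 1 and 3 a symptom scored 3 or 4 triggers an alert. That is the same cut that defines 4c and 5c. The outcome window runs from the day before to the day after the day-5 assessment, so it opens before the selecting score is taken. A child whose symptom is charted and treated on day 4 and who then improves can drop out of the subset, while an untreated child stays in. Successful care can then look like absent care. If relief instead removes mainly undocumented children, the intervention looks better than it is.

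At stake is how Aim 3 is read. A difference, or the lack of one, in these subsets could be published as a treatment effect on provider behaviour when it reflects who remained symptomatic.

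**Working it through.** **How much of Aim 3 is involved.** Two outcomes x 3 sets x 15 symptoms = 90 comparisons. Sets b and c make up 2 x 2 x 15 = 60.

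**The plan's own figure.** The plan gives no figure on this point. Its only design calculation is for the primary outcome (difference 2.7, SD 8.5, 80% power, alpha 0.05). It reproduces: 2 x (8.5 x (1.960 + 0.842)/2.7)² = 155.6 per arm, or 156.5 with the t distribution, hence 157. I use 157 below only to gauge subset sizes.

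**Model 1: relief removes children from the subset.** Let d be the share documented before anyone leaves, q the share of documented children who fall below the cut by day 5, and u the same share for undocumented children. Documentation in the selected subset is then

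d(1-q) / [d(1-q) + (1-d)(1-u)].

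The values of d come from Preliminary Data: 18% for severe fatigue, and 62% for mouth sores (the latter is not a rate at a score of 3 or more). All q and u are assumptions. If q = u the formula returns d exactly.

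*No true effect on documentation* (same d in both arms; differences from unrounded rates):

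| Leaving, control vs intervention | d = 18% | d = 62% |
|---|---|---|
| documented, 10% vs 20% | 16.5% vs 14.9% = -1.6 | 59.5% vs 56.6% = -2.9 |
| documented, 30% vs 50% | 13.3% vs 9.9% = -3.4 | 53.3% vs 44.9% = -8.4 |
| documented, 30% vs 70% | 13.3% vs 6.2% = -7.1 | 53.3% vs 32.9% = -20.5 |
| undocumented, 30% vs 50% | 23.9% vs 30.5% = +6.6 | 70.0% vs 76.5% = +6.6 |

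Example: 0.18 x 0.7 / (0.18 x 0.7 + 0.82) = 0.126/0.946 = 13.3%. Swapping the arms reverses the sign. Equal relief in both arms gives zero.

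*True gain of 20 points before anyone leaves* (u = 0):

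| Documented children leaving | 18% to 38% | 62% to 82% |
|---|---|---|
| 30% vs 30% | +16.7 | +22.8 |
| 30% vs 70% | +2.2 | +4.4 |
| 70% vs 30% | +23.8 | +43.3 |

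For a gain from 40% to 60% with 30% vs 70% relief, the subset shows 31.8% vs 31.0%, or -0.8: a real gain disappears.

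**Model 2: a separate check.** Take severe fatigue at 33% (Background) and 18% documentation, with no effect of arm on anyone's documentation. Let the intervention move a share r of would-be severe children below 3, and let those children be documented k times as often as those who stay severe. Documentation among the selected intervention children is 0.18 / [(1-r) + rk].

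- k = 0.5, r from 0.1 to 0.4: +0.9 to +4.5 points (odds ratio 1.06 to 1.32).
- k = 2, r from 0.1 to 0.4: -1.6 to -5.1 points (odds ratio 0.89 to 0.67).
- k = 1: zero.

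Subset sizes are about 157 x 0.33 = 52 control and 47 (r = 0.1) to 31 (r = 0.4) intervention.

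**Model 3: latent-severity simulation.** With an assumed shift of 2.7/8.5 = 0.32 SD in one symptom and no effect on documentation, 33% of controls and 22% of the intervention arm are selected. Documentation among the selected is 34.5% vs 37.7% if it rises with severity, 11.5% vs 10.0% if it falls, and 18.2% in both arms if unrelated. The all-participant comparison, as in 4a, stays null throughout.

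**The case against.** The strongest reply is that the plan already contains the right comparison. Sets 4a and 5a cover all participants and come first, the other four are described as more exploratory, and nothing bases a confirmatory claim on them. This limits the seriousness but does not remove the point. The exploratory label is used to justify working with observed data; the odds ratios, p-values and treatment-effect wording remain, and sets a, b and c are listed in parallel with the same inference.

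The size may well be small. At the other documentation rates under Preliminary Data, Model 1 with no true effect and 30% vs 50% relief gives -0.6 points at 3%, -2.0 at 10% and -3.0 at 94%. At 0% or 100% it gives nothing; those are the reported intervention rates for severe fatigue and for pain. The simulation gives only +3.2, -1.5 or 0 points, against a standard error of about 8 to 9 points in a severe-fatigue subset: the root of 0.18 x 0.82 x (1/52 + 1/47) is 7.7 points, and 8.7 with 31 in place of 47. All of this is correct. It bears on magnitude, not on whether the comparison is randomized.

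Some scenarios are also less natural. Relief of 70% vs 30% runs against the trial's hypothesis, and the plan does not name the before-leaving population as its target. The day-4 route is weakened because day-6 entries cannot have lowered the day-5 score, and a recall period of yesterday or today may keep a symptom relieved on day 4 in the subset. Care charted only on days 1 to 3 lies outside the window.

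The statement under Protecting against Bias arises from contamination and covers these data in general. It shows that Aim 3 data will inform interpretation, not that the subsets specifically will.

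Finally, whether a symptom reported now is also charted or treated now is a sensible process question. I agree, and the fix keeps it.

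**Conclusion.** The concern holds. Four of the six Aim 3 analysis sets condition on a post-randomization outcome that the trial expects to change, and the plan attaches between-arm inference to them without a caveat. Bias needs two conditions: assignment changes who is selected, and that change is related to documentation or treatment. If either fails, it is zero. Neither size nor direction can be derived from the documents. The figures above are illustrations under assumed relief shares, not bounds.

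Confidence is high on the structural point only. This should be corrected, but it is confined to secondary analyses: the primary analysis, outcomes 1 to 3, and 4a and 5a stand as they are.

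**What to change.** 1. State in the Analytic Plan that 4a and 5a are the randomized comparisons for Aim 3.
2. Report 4b, 4c, 5b and 5c as descriptive process measures by arm, with the number selected in each arm. Drop the between-arm odds ratios, p-values and treatment-effect wording for these sets, and say that they will not be used as evidence of an effect of assignment.

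Both are wording changes, with no new data and no change to sample size. The price is that no formal test remains among children symptomatic on day 5, and that 4a and 5a include children without the symptom, so they show the total effect of assignment rather than the response to a given symptom.

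Optional: if inference in symptomatic children is wanted, pre-specify subsets by the day-1 symptom score. The documents do not say whether that score is obtained before allocation is known; if it is not, a procedural change would be needed. These subsets answer a different question. They estimate the total effect of assignment, and symptoms resolved by day 5 will tend to count as not documented or not treated, so faster resolution in the intervention arm could appear as less documentation. The statement "There are no planned subgroup analyses" would have to be revised to match.
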